8.2. Secondary Safety Analyses

8.2.1. Overview of Planned Secondary Safety Analyses

The secondary safety analyses will be based on the Safety population, unless otherwise specified.

Table 7 provides an overview of the planned secondary safety analyses, with further details of data displays being presented in Section [11.15](#).

Table 7 Overview of Planned Secondary Safety Analyses

Endpoints	Absolute				Change from Baseline			
	Summary		Individual		Summary		Individual	
	T	F	F	L	T	F	F	L
Adverse Events								
All cause mortality (time to death)	Y (x3)[1]	Y (x3)[1]			Y[1]			
AE Overview	Y (x2)							
Serious adverse events (SAE)	Y (x4) [2]							
Reason for Seriousness				Y				
All AEs planned to be collected	Y (x4) [2]							
Treatment related AEs planned to be collected	Y [3]							
AEs planned to be collected by subgroup	Y (x3) [4]							
AEs planned to be collected by maximum intensity	Y (x3) [5]							
Common ($\geq 2\%$) AEs planned to be collected	Y (x2) [6]							
All reported AEs	Y (x2) [6]			Y				
Reported AEs for subjects with baseline eGFR <30				Y				
Fatal SAEs, Nonfatal SAEs	Y (x4) [7]			Y (x2)				
Treatment-related SAEs, Treatment-related fatal SAEs	Y (x2) [3]							
Common ($\geq 2\%$) SAEs	Y (x2)[8]	Y						
SAEs by Subgroup	Y (x3) [4]							
AE leading to discontinuation of IP: Overall, serious	Y (x2)			Y [9]				
Non-serious AEs not AESIs nor led to				Y				

Endpoints	Absolute				Change from Baseline			
	Summary		Individual		Summary		Individual	
	T	F	F	L	T	F	F	L
discontinuation of IP								
Subject Numbers for Individual AEs				Y [10]				
Relationship between AE SOCs, PT and Verbatim Text				Y [10]				
AEs of special interest (AESIs): Overview	Y (x2) [11]	Y						
AEs of special interest: Development of thyroid cancer [12], Haematologic malignancy, Pancreatic cancer, Investigator-reported Pancreatitis [12], Investigational Product injection site reactions [12], Immunological reactions [12], Severe hypoglycaemic events [12], Hepatic events, Hepatic enzyme elevations (including GGT), Serious gastrointestinal (GI) events, Appendicitis, Atrial fibrillation/flutter [12], Pneumonia [12], Worsening renal function [12], Diabetic retinopathy [12]	Y (x69) [13]	Y (x2) [14]		Y (x10) [15]				
Immunogenicity data	Y (x2)			Y (x4)				
AEs of Special Interest: Adjudicated Pancreatitis	Y (x5) [16]			Y (x2)				
AEs of Special Interest: severe hypoglycaemic events by baseline HbA1c, eGFR, age, and sulfonylurea(SU) / insulin	Y (x8) [17]							
AEs of Special Interest: Recurrent event analysis of Severe Hypoglycaemic events	Y (x4) [18]							

Endpoints	Absolute				Change from Baseline			
	Summary		Individual		Summary		Individual	
	T	F	F	L	T	F	F	L
Malignant neoplasms	Y (x10) [19]			Y				
Other significant AEs				Y				
Liver monitoring/stopping events	Y [20]			Y (x5)				
Hepatobiliary Abnormalities	Y [3]			Y				
Liver Function Tests of Potential Clinical Concern	Y							
AEs of Special Interest Overview by Subgroup	Y (x3) [21]							
AEs of Special Interest by Subgroup (Age, Sex)	Y (x4)							
Other								
eGFR [22]	Y (x2) [23]	Y			Y (x3)	Y (x2) [24]		Y [22]
eGFR (Central Lab only) [25]					Y (x2)			
BP and heart rate	Y (x2) [26]	Y (x3)			Y (x3) [27]	Y (x3)		Y [28]

NOTES :

- T = Table, F = Figure, L = Listing, Y = Yes display generated.
- Summary = Represents TFL related to any summaries (i.e. descriptive statistics) of the observed raw data.
- Individual = Represents FL related to any displays of individual subject observed raw data.

[1] ITT Population; for vital status follow-up, On-therapy, and On-treatment time periods.

[2] Frequency for On-therapy and Post-therapy combined, On-therapy, time periods (SOC and Preferred Terms, and also SOC, high level term (HLT) and Preferred Terms).

[3] Frequency for On-therapy time period.

[4] Subgroups are Age, Sex, eGFR; frequency overall and by system organ class (SOC) and HLT for the On-therapy time period.

[5] On-therapy and post-therapy combined, on-therapy, and on-therapy treatment-related.

[6] Frequency for On-therapy and Post-therapy combined, On-therapy time periods.

[7] For each type: Frequency for On-therapy and Post-therapy combined, On-therapy, time periods (SOC and Preferred Terms).

[8] Frequency for On-therapy and Post-therapy combined, On-therapy time periods (Preferred Terms).

[9] Includes any AE leading to discontinuation of IP.

[10] Includes all reported AEs/SAEs.

[11] On-therapy and Post-therapy combined, On-therapy time periods (eCRF event specific page or defined list of terms).

[12] Event-specific details recorded.

[13] Frequency overall and by SOC and Preferred Term, along with summary of characteristics, each done for On-therapy and Post-therapy combined, On-therapy time periods; also details for AESI with event-specific page for On-therapy time period.

[14] Kaplan-Meier plots for serious GI events and Investigational Product Injection Site reactions only, On-therapy time period.

[15] Listings of event-specific details will be provided for appropriate AESIs, along with AE listings for all AESIs.

- [16] Frequency overall and by SOC and Preferred Term (PT), each done for On-therapy and Post-therapy combined, On-therapy time periods for events adjudicated as definite or possible; adjudication details done for On-therapy and Post-therapy combined, On-therapy time periods; summary of characteristics for On-therapy events adjudicated as definite or possible.
- [17] Frequency for On-therapy and Post-therapy combined, On-therapy time periods for each of 4 subgroups.
- [18] Analysis for On-therapy and On-treatment time periods, each overall and stratified by baseline SU/Insulin use.
- [19] Frequency for On-therapy and Post-therapy combined, On-therapy time periods by SOC, HLT and PT; overall, by insulin use at baseline, by history of malignancy at baseline; also corresponding Mantel-Haenszel tests by insulin use at baseline, by history of malignancy at baseline.
- [20] On-therapy and Post-therapy combined time period.
- [21] Subgroups are Age, Sex, eGFR for AESIs for which incidence is $\geq 1.0\%$ in either treatment group; frequency for the On-therapy time period.
- [22] Computed using MDRD formula per protocol; including baseline local and Central lab creatinine data and post-baseline scheduled visit Central lab creatinine data.
- [23] Raw, categories.
- [24] Plots of raw means vs time and also adjusted means vs time.
- [25] Computed using MDRD formula per protocol; including baseline and post-baseline scheduled visit Central lab creatinine data.
- [26] Raw, potential clinical concern.
- [27] Change from baseline, potential clinical concern, shift table.
- [28] Listing includes value and change from baseline; for BP and heart rate only including subjects with values of potential clinical concern.

All serious adverse events, including deaths, will be recorded in the eCRF, as well as AEs leading to discontinuation of IP and AEs of special interest (AESI). MI, stroke, unstable angina requiring urgent revascularization, hospitalization for heart failure, TIA and sudden cardiac death will not be recorded as AEs or SAEs, but will instead be recorded on event-specific eCRF forms. For some AESIs (development of thyroid cancer, pancreatitis, investigational product injection site reactions, immunological reactions, severe hypoglycaemic events, atrial fibrillation/flutter, pneumonia, worsening renal function, diabetic retinopathy), additional event-specific details are also recorded in the eCRF; summaries of incidence will be provided based on these data. For the remaining AESIs, summaries of incidence will be based on defined lists of coded terms. Summaries of the AESI event-specific details will also be provided. For AESIs with incidence $\geq 1.0\%$ in either treatment group, summaries of incidence at the highest level will be provided by baseline eGFR ($\geq 90, \geq 60$ to $< 90, < 60$ ml/min/1.73m²), age ($< 65, \geq 65$ to $< 75, \geq 75$ years), and sex (female, male) subgroups. For severe hypoglycemic events, summaries of incidence will be provided by baseline HbA1c ($< 8.0\%, \geq 8.0\%$ to $< 9.0\%, \geq 9.0\%$), baseline eGFR ($\geq 90, \geq 60$ to $< 90, < 60$ ml/min/1.73m²), age ($< 65, \geq 65$ to $< 75, \geq 75$ years), and baseline sulfonylurea/insulin use (yes, no) subgroups. Data related to liver monitoring/stopping event reporting are recorded in the eCRF. Additional detail regarding definitions used to identify the AESIs are provided in Section 11.6.3.

For subjects treated with albiglutide, the frequency of immunological reaction AESIs will be summarized for the On-therapy and Post-therapy combined time period by anti-albiglutide antibody status (positive, negative, unknown) and also by IgE antibody status (positive, negative, unknown).

Frequency of malignant neoplasms (non-serious AEs or SAEs) will be summarized overall, by insulin use at baseline (yes, no), and by history of malignancy at baseline (yes, no). See Section 11.6.3 regarding definitions to be used to identify malignant neoplasms.

8.2.2. Planned Secondary Safety Statistical Analyses

Statistical Analyses
Endpoints

 • All cause mortality (time to death) • Non-fatal SAEs • AEs of special interest • eGFR (computed)
Model Specification

 • For time to death, analysis will be done in a similar manner as the primary endpoint: treatment group comparisons for the ITT population will be done using the Wald test p-value from a Cox Proportional Hazards regression model with treatment group as the only covariate. For time to death, an estimate of the hazard ratio and 95% confidence interval will be presented, along with Kaplan-Meier (KM) curves by treatment group. Frequency of death will be summarized for the vital status follow-up, On-therapy, and On-treatment time periods. • For each common SAE (i.e., those Preferred Terms with frequency $\geq 2\%$ in either treatment group) frequency of occurrence by Preferred Term will be summarized for the On-therapy and Post-therapy combined, and On-therapy time periods, and the relative risk and 95% confidence interval will be computed. The relative risk for an event will be defined as the ratio of the probability of a subject in the albiglutide treatment group having at least 1 event to the probability of a subject in the placebo treatment group having at least 1 event. PROC FREQ in SAS will be used to compute relative risk and the associated exact unconditional confidence interval. In addition, AE density and incidence rates per 100 person years (PY) by Preferred Term will be computed. A plot of relative risk and 95% CI will be produced for the most common SAEs for the On-therapy time period. • For each common (i.e., those Preferred Terms with frequency $\geq 2\%$ in either treatment group) AE planned to be collected (SAEs, AEs leading to discontinuation of IP, and AESIs), frequency of occurrence by Preferred Term will be summarized for the On-therapy and Post-therapy combined, and On-therapy time periods. • For each AESI (including Investigator-reported pancreatitis and adjudicated pancreatitis) frequency of occurrence by SOC and Preferred Term will be summarized for the On-therapy and Post-therapy combined, and On-therapy time periods, and the relative risk and 95% confidence interval will be computed as previously described. In addition, AE density and incidence rates per 100 PY will be computed. Intensity, seriousness, relationship to IP, action taken, outcome, time relative to treatment start, time relative to treatment stop, and event duration will be summarized. A plot of relative risk and 95% CI will be produced for the AESI based on the On-therapy time period. Time to first AESI for the On-therapy time period will be summarized using KM curves by treatment group for serious GI events and Investigational Product Injection Site reactions. • For malignant neoplasms during the On-therapy and Post-therapy combined time periods, treatment group comparisons will be done with the nonparametric, extended Mantel-Haenszel test adjusting for baseline insulin use (yes, no) using the SAS FREQ procedure. As a sensitivity analysis, this will also be done for the On-therapy time period. These analyses will also be done adjusting for baseline history of malignancy (yes, no).

Statistical Analyses

 For severe hypoglycaemic events during the On-therapy time period an additional recurrent event analysis will be performed in a manner similar to that done for MACE (see Section 7.1.2). As a sensitivity analysis, this will also be done for the On-treatment time period. It is recognized that sulfonylurea /insulin use may increase risk of hypoglycaemic events; hence the recurrent events analysis will be also be done stratified by baseline sulfonylurea/insulin use (yes, no). Summaries and analyses of eGFR will be based on values from scheduled visits computed using the protocol-specified formula based on the measured creatinine, including baseline local and Central lab creatinine data and post-baseline scheduled visit Central lab creatinine data. For change from baseline eGFR, treatment group comparisons will be done using a MMRM analysis as previously described using an On-treatment analysis. Due to the event-driven nature of the study, beyond Month 16 only summary statistics will be provided. In addition, eGFR will be categorically summarized by visit as Normal ≥ 90, Mild ≥ 60 to < 90, Moderate ≥ 30 to < 60, and Severe < 30. Shift tables of eGFR from baseline to post-baseline planned relative timepoints will be provided including a summary of the shifts to the most severe eGFR category determined post-baseline. 
Sensitivity analyses will be done using the protocol-specified equation and measured creatinine, including baseline and post-baseline scheduled visit Central lab creatinine data. These will include the MMRM analysis and the shift tables.

Model Results Presentation

 For time to event endpoints, p-values and estimates of hazard ratios and 95% confidence intervals (CIs) will be presented, along with Kaplan-Meier (KM) curves by treatment group. For change from baseline endpoints, least square means, 95% CIs and nominal p-values will be presented, along with plots of least square means vs time by treatment group.

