- AE density, also referred to as event density, will be calculated for specified AEs. AE density = number of events / AE density person-years and will be presented per 100 person-years.
- AE density person-years = cumulative total of censoring time / 365.25, where censoring time is the censoring date – treatment start date + 1. Censoring date will be assigned based on the evaluation time period of interest as subsequently specified.

Time Period for On-treatment AEs

The time period for capturing On-treatment AEs begins at treatment start date. The end of this time period is the earliest of the following two dates: treatment stop date, latest of clinic visits, phone calls and other contact with subject.

Any events that occurred before the start of this time period are considered to be prior to the time period for On-treatment AEs, and any events that occurred after the end of this time period are considered to be post the time period for On-treatment AEs.

Time Period for On-therapy AEs

The time period for capturing On-therapy AEs begins at treatment start date. The end of this time period is the earliest of the following two dates: treatment stop date + 56 days and latest of clinic visits, phone calls and other contact with subject.

Any events that occurred before the start of this time period are considered to be prior to the time period for On-therapy AEs, and any events that occurred after the end of this time period are considered to be post the time period for On-therapy AEs.

Time Period for On-therapy and Post-therapy AEs
--

The time period for capturing On-therapy and Post-therapy AEs begins at treatment start date. The

end of this time period is the latest of the following: latest of clinic visits, phone calls and other contact with subject, latest non-missing AE start date, latest non-missing AE end date.

Any events that occurred before the start of this time period are considered to be prior to the time period for On-therapy and Post-therapy AEs, and any events that occurred after the end of this time period are considered to be post the time period for On-therapy and Post-therapy AEs.

AEs of Special Interest

Following are the protocol-specified AEs of special interest:

- Development of thyroid cancer
- Haematologic malignancy
- Pancreatic cancer
- Pancreatitis
- Investigational Product Injection site reactions
- Immunological reactions
- Severe hypoglycaemic events
- Hepatic events
- Hepatic enzyme elevations (including GGT)

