11.15.7. Safety Figures

Figure No.	Title	Population	Programming note
3.01	Kaplan-Meier Plot of Time to Death (Vital Status Follow-up Time Period)	ITT	
3.02	Kaplan-Meier Plot of Time to Death (On-therapy Time Period)	ITT	
3.03	Kaplan-Meier Plot of Time to Death (On-treatment Time Period)	ITT	
3.04	Common (>=2%) On-therapy Serious Adverse Events Sorted by Relative Risk	Safety	
3.05	On-therapy Adverse Events of Special Interest Sorted by Relative Risk	Safety	
3.06	Kaplan Meier Plot of Time to First Investigational Product Injection Site Reaction (On-therapy Time Period)	Safety	
3.07	Kaplan Meier Plot of Time to First Serious GI Event (On-therapy Time Period)	Safety	
3.08	Line Graph of Mean (+/-SE) eGFR (ml/min/1.73m ²) Over Time	Safety	
3.09	Line Graph of Mean (+/-SE) Change from Baseline eGFR (ml/min/1.73m ²) Over Time	Safety	
3.10	Line Graph of Adjusted Mean (+/-SE) Change from Baseline On-treatment eGFR (ml/min/1.73m ²) Over Time	Safety	Plot adjusted means.
3.11	Line Graph of Mean (+/-SE) SBP (mmHg) Over Time	Safety	
3.12	Line Graph of Mean (+/-SE) Change from Baseline SBP (mmHg) Over Time	Safety	
3.13	Line Graph of Mean (+/-SE) DBP (mmHg) Over Time	Safety	
3.14	Line Graph of Mean (+/-SE) Change from Baseline DBP (mmHg) Over Time	Safety	

Figure No.	Title	Population	Programming note
3.15	Line Graph of Mean (+/-SE) Heart Rate (bpm) Over Time	Safety	
3.16	Line Graph of Mean (+/-SE) Change from Baseline Heart Rate (bpm) Over Time	Safety	
3.17	Scatter Plot of Maximum vs. Baseline for ALT	Safety	
3.18	Scatter Plot of Maximum Total Bilirubin versus Maximum ALT - eDISH	Safety	
3.19	Box Plot of Creatinine (umol/l) Over Time	Safety	
3.20	Box Plot of Change from Baseline Creatinine (umol/l) Over Time	Safety	

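### For common SAEs and most AESIs, the only On-therapy between-arm contrast with a CI is a ratio of crude proportions, which shifts toward the arm that stops treatment earlier; a person-time ratio should be added

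*SAP*

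**What the plan says.** **Estimator.** Section 8.2.2 defines the measure for common SAEs: "The relative risk for an event will be defined as the ratio of the probability of a subject in the albiglutide treatment group". The numerator is thus the share of albiglutide subjects with any event, and the denominator is the placebo share. The method is a 2x2 table: "PROC FREQ in SAS will be used to compute relative risk and the associated exact unconditional confidence interval". AESIs are handled the same way.

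**Window.** Section 11.6.3 starts the On-therapy AE period at treatment start and ends it at the earlier of "treatment stop date + 56 days and latest of clinic visits, phone calls and other contact with subject". Section 11.4.2 classifies AEs by the same 56-day rule.

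**Displays.** Section 8.2.2 plans two plots: "A plot of relative risk and 95% CI will be produced for the most common SAEs for the On-therapy time period", and "A plot of relative risk and 95% CI will be produced for the AESI based on the On-therapy time period". These are Figures 3.04 and 3.05; the second is titled "On-therapy Adverse Events of Special Interest Sorted by Relative Risk".

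**Companion measures.** The same section adds, for common SAEs, "In addition, AE density and incidence rates per 100 person years (PY) by Preferred Term will be computed", and likewise plans both measures for AESIs. Section 11.6.3 defines first-AE person-years for the incidence rate. The relative risk is also computed for On-therapy and Post-therapy combined.

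**The concern.** A crude proportion is comparable between arms only if subjects are observed for similar lengths of time. Randomization makes potential follow-up comparable, but the On-therapy window is cut by each subject's own stopping. A subject who stops early stays in the denominator while later events leave the numerator. If one arm stops more often, it has less time to record every other event, and the ratio falls for that reason alone.

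At stake is how harm is read from the main relative-risk displays. The SAP adjusts for time elsewhere: On-therapy MACE and On-therapy death have time-to-event analyses, and severe hypoglycaemia has a negative binomial model with a log follow-up offset (section 8.2.2, by reference to 7.1.2). Common SAEs and the other AESIs have no such contrast over the same window. Two AESIs, injection site reactions and serious GI events, have Kaplan-Meier curves only.

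**Working it through.** The SAP states no figure on this point. Its one design figure does reproduce: 4 x (1.960 + 1.2816)^2 / (ln 1.3)^2 = 610.6, or 611 events. It does not enter what follows.

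**Inputs from the SAP:** the crude ratio of proportions; a window ending at stop date + 56 days, or 56/365.25 = 0.1533 years; projected median follow-up of at least 1.5 years.

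**Assumed, because the SAP does not give them:** common follow-up F of 1.5 or 2.0 years; exponential stopping times, with 20% of placebo and 20-40% of albiglutide subjects stopping by F; a constant event hazard of 2 or 5 per 100 person-years.

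**Formulas.** Stopping rate d = -ln(1 - proportion stopping)/F. On-therapy time T = min(stop time + 0.1533, F). Its mean is 0.1533 + [1 - exp(-d(F - 0.1533))]/d. The expected crude proportion is the mean of 1 - exp(-hazard x T).

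**Worked case, F = 1.5, 30% vs 20% stopping.**
- Placebo: d = -ln(0.80)/1.5 = 0.1488; mean T = 0.1533 + 1.2203 = 1.374 years.
- Albiglutide: d = -ln(0.70)/1.5 = 0.2378; mean T = 0.1533 + 1.1524 = 1.306 years.
- At 5 per 100 person-years in both arms the expected proportions are 0.0630 and 0.0663. Their unrounded ratio is 0.951, close to the ratio of mean times, 1.306/1.374 = 0.95.

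**All cases at F = 1.5, placebo stopping 20%** (ranges cover the two event rates):

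| Albiglutide stopping | Mean On-therapy years (placebo 1.374) | Ratio of mean times | Crude RR, true HR 1.00 | Crude RR, true HR 1.10 |
|---|---|---|---|---|
| 20% | 1.374 | 1.00 | 1.000 | 1.096-1.098 |
| 25% | 1.340 | 0.98 | 0.976 | 1.070-1.072 |
| 30% | 1.306 | 0.95 | 0.951 | 1.043-1.044 |
| 35% | 1.270 | 0.92 | 0.925-0.926 | 1.015-1.016 |
| 40% | 1.233 | 0.90 | 0.899 | 0.986-0.987 |

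At F = 2.0 and true HR 1.00, the last four rows give about 0.974, 0.948, 0.921 and 0.893. Under a constant hazard the expected first-event rate per person-year equals the hazard in each arm, so a person-time ratio returns 1.00 in every row with true HR 1.00.

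**Timing of events, F = 1.5, 30% vs 20%, true HR 1.00.** With a hazard of 0.20 per year for three months and 0.005 afterwards, the crude RR is 0.993. With events only after one year, at 0.05 per year, it is 0.907.

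**The case against.** The strongest reply is that the SAP already lets a reader see the problem. Incidence rates per 100 person-years stand beside the relative risk in Tables 3.034 and 3.040. Stopping and exposure are reported in Tables 1.11 and 1.49 and Figure 1.02. Tables 3.033 and 3.039 give a relative risk with CI for the combined period, which does not end at stopping, and follow-up is meant to continue after discontinuation (section 11.2.2). The probability of an event while on therapy is also a legitimate descriptive quantity, and no formal decision rests on it.

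Most of that stands. It is a reason to add a measure rather than replace one. It does not close the gap: per-arm rates carry no contrast or CI, and the combined period includes time off drug and so answers a different question. The subgroup overviews in Tables 3.041-3.043 have no combined-period counterpart.

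Two stronger readings are tempting but unsupported.
- A reader might infer that no time-adjusted safety contrast with a CI is planned at all. Death has a Cox hazard ratio, and severe hypoglycaemia, itself an AESI, has an exposure-adjusted ratio with confidence limits.
- A reader might infer that the displays will hide a real harm of albiglutide. The SAP says nothing about which arm stops earlier. If placebo does, harm is overstated. In the cases above, a true 1.10 falls below 1 only at 40% vs 20% stopping. Where the event itself causes stopping, as an injection site reaction may, the distortion takes a different form.

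**Conclusion.** The concern holds as a gap in the planned contrasts and plots. For common SAEs and for AESIs other than severe hypoglycaemia, the On-therapy comparison with a CI depends on time on drug as well as on event rate, and Figures 3.04-3.05 show nothing else.

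The shift is roughly the ratio of mean On-therapy times. Under the stated assumptions it is 2-3% for a 5-point stopping imbalance, about 5% for 10 points and 10-11% for 20 points. It is zero if stopping is balanced, near nil for early-onset events and larger for late ones. The mechanism follows from the SAP's definitions; the size rests on stopping rates and hazards that the SAP does not contain. The primary endpoint is unaffected. This is an inexpensive improvement, not a flaw that invalidates the safety analysis.

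**What to change.** In section 8.2.2, and in Tables 3.034 and 3.040-3.043, add beside the On-therapy relative risk one time-adjusted contrast with a 95% CI. It can be the incidence rate ratio (subjects with a first event divided by first-AE person-years, albiglutide over placebo) or a Cox hazard ratio censored at the end of the On-therapy period. Choose one before unblinding and plot it in Figures 3.04 and 3.05. Keep the crude relative risk, including for On-therapy and Post-therapy combined.

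The cost is a few sentences of SAP text and a small programming change, since first-AE person-years are already derived for the incidence rates. The limits should be stated: the rate ratio assumes a roughly constant rate, and neither measure removes bias when stopping is related to the risk of the event. No dosing, stopping or other clinical management rule is touched.

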3.038	Summary of On-therapy Serious Adverse Events Leading to Permanent Discontinuation of Study Treatment by SOC and PT	Safety	SOC and PT, #/% of subjects and # of events, event density

Table No.	Title	Population	Programming note
3.039	Overview of On-therapy and Post-therapy Adverse Events of Special Interest	Safety	#/% of subjects, incidence rate (subjects/100PY) and # of events and event density (events/100PY): overall for each type of AESIs, relative risk (95% CI) - includes incidence based on CMQ/ SMQ for AESIs that do not have event-specific page, otherwise based on event-specific page only.
3.040	Overview of On-therapy Adverse Events of Special Interest	Safety	As per 8A, above.
3.041	Overview of On-therapy Adverse Events of Special Interest by Baseline eGFR (Incidence $\geq 1\%$ in Either Treatment Group)	Safety	As per 8A eGFR subgroups (<60 , ≥ 60 to <90 , ≥ 90 ml/min/1.73m ²)
3.042	Overview of On-therapy Adverse Events of Special Interest by Sex (Incidence $\geq 1\%$ in Either Treatment Group)	Safety	As per 8A.
3.043	Overview of On-therapy Adverse Events of Special Interest by Age (Incidence $\geq 1\%$ in Either Treatment Group)	Safety	As per 8A. <65 , ≥ 65 to <75 , ≥ 75 years
3.044	Summary of On-therapy and Post-therapy AESIs by Age	Safety	SOC and PT, #/% of subjects and # of events, event density

Table No.	Title	Population	Programming note
3.045	Summary of On-therapy AESIs by Age	Safety	SOC and PT, #/% of subjects and # of events, event density
3.046	Summary of On-therapy and Post-therapy AESIs by Sex	Safety	SOC and PT, #/% of subjects and # of events, event density
3.047	Summary of On-therapy AESIs by Sex	Safety	SOC and PT, #/% of subjects and # of events, event density
3.048	Overview of On-therapy and Post-therapy AESIs: Thyroid Cancer Diagnosis	Safety	
3.049	Summary of On-therapy and Post-therapy AESIs: Thyroid Cancer Diagnosis, by SOC and PT	Safety	SOC and PT, #/% of subjects and # of events, event density
3.050	Overview of On-therapy AESIs: Thyroid Cancer Diagnosis	Safety	
3.051	Summary of Investigator-reported Characteristics of On-therapy AESIs of Thyroid Cancer Diagnosis	Safety	
3.052	Summary of On-therapy AESIs: Thyroid Cancer Diagnosis, by SOC and PT	Safety	SOC and PT, #/% of subjects and # of events, event density
3.053	Overview of On-therapy and Post-therapy AESIs: Haematologic Malignancy	Safety	

Table No.	Title	Population	Programming note

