3.129	Summary of On-therapy Severe Hypoglycaemic Events by Age at Baseline, SOC and PT	Safety	SOC and PT, #/% of subjects and # of events, event density age (<65, ≥65 to <75, ≥75 years)
3.130	Summary of On-therapy and Post-therapy Severe Hypoglycaemic Events by Baseline Sulfonylurea/Insulin Use, SOC and PT	Safety	SOC and PT, #/% of subjects and # of events, event density Baseline sulfonylurea/insulin use = Yes or No
3.131	Summary of On-therapy Severe Hypoglycaemic Events by Baseline Sulfonylurea/Insulin Use, SOC and PT	Safety	SOC and PT, #/% of subjects and # of events, event density Baseline sulfonylurea/insulin use = Yes or No
3.132	Summary of Recurrent Event Analysis of On-therapy Severe Hypoglycaemic Events	Safety	
3.133	Summary of Recurrent Event Analysis of On-treatment Severe Hypoglycaemic Events	Safety	
3.134	Summary of Recurrent Event Analysis of On-therapy Severe Hypoglycaemic Events (Adjusting for Baseline Sulfonylurea/Insulin Use)	Safety	

Table No.	Title	Population	Programming note
3.135	Summary of Recurrent Event Analysis of On-treatment Severe Hypoglycaemic Events (Adjusting for Baseline Sulfonylurea/Insulin Use)	Safety	
3.136	Summary of On-therapy and Post-therapy Malignant Neoplasms by SOC, HLT and PT	Safety	SOC, HLT and PT, #/% of subjects and # of events, event density
3.137	Summary of On-therapy Malignant Neoplasms by SOC, HLT and PT	Safety	SOC, HLT and PT, #/% of subjects and # of events, event density
3.138	Summary of On-therapy and Post-therapy Malignant Neoplasms by Insulin Use at Baseline, SOC, HLT and PT	Safety	SOC, HLT and PT, #/% of subjects and # of events, event density
3.139	Summary of Mantel-Haenszel Analysis of On-therapy and Post-therapy Malignant Neoplasms, Stratified by Insulin Use at Baseline	Safety	
3.140	Summary of On-therapy Malignant Neoplasms by Insulin Use at Baseline, SOC, HLT and PT	Safety	SOC, HLT and PT, #/% of subjects and # of events, event density
3.141	Summary of Mantel-Haenszel Analysis of On-therapy Malignant Neoplasms, Stratified by Insulin Use at Baseline	Safety	
3.142	Summary of On-therapy and Post-therapy Malignant Neoplasms by History of Malignancy at Baseline, SOC, HLT and PT	Safety	SOC, HLT and PT, #/% of subjects and # of events, event density
3.143	Summary of Mantel-Haenszel Analysis of On-therapy and Post-therapy Malignant Neoplasms, Stratified by History of Malignancy at Baseline	Safety	

Table No.	Title	Population	Programming note

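### Overall malignant neoplasms are compared between arms by a stratified Mantel-Haenszel test with no relative risk or confidence interval, unlike AESIs and common SAEs in the same section

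*SAP*

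**What the plan says.** Section 8.2.2 sets out the comparison of malignant neoplasms for the combined on-therapy and post-therapy period: "treatment group comparisons will be done with the nonparametric, extended Mantel-Haenszel test adjusting for baseline insulin use (yes, no) using the SAS FREQ procedure". It repeats this for the on-therapy period as a sensitivity analysis, and does both again adjusting for history of malignancy. Table 7 note [19] lists frequencies and "also corresponding Mantel-Haenszel tests by insulin use at baseline, by history of malignancy at baseline".

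The display list in Section 11.15.6 follows the same line. Table 3.139 is titled "Summary of Mantel-Haenszel Analysis of On-therapy and Post-therapy Malignant Neoplasms, Stratified by Insulin Use at Baseline"; Tables 3.141, 3.143 and 3.145 are its counterparts for the other period and stratifier. All four have empty programming notes. The descriptive tables (3.136–3.138, 3.140, 3.142, 3.144) carry the note "SOC, HLT and PT, #/% of subjects and # of events, event density".

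Other event groups are handled differently in the same section. For each common SAE term a relative risk and 95% CI are planned, and "PROC FREQ in SAS will be used to compute relative risk and the associated exact unconditional confidence interval". For each AESI, "the relative risk and 95% confidence interval will be computed as previously described". Three cancers are on that list: "AEs of special interest: Development of thyroid cancer [12], Haematologic malignancy, Pancreatic cancer".

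**The concern.** A safety comparison should say how large an excess of harm the data rule out. A test alone says only whether the observed difference passes a significance threshold, and Section 8.2.2 stops at the test for overall malignancy. The trial size was set by the MACE endpoint, so nothing in the SAP assures that a non-significant malignancy test is informative. A large p-value would be compatible both with a tight interval around 1 and with a wide one reaching well above it, and the planned inferential output does not distinguish the two.

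Where the SAP wants an estimate it says so, both in the text of 8.2.2 and in the programming notes of Tables 3.033, 3.034 and 3.039. The omission is therefore specific to this grouping.

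**Working it through.** **Step 1: does another rule supply the estimate?**

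| Rule in Section 8.2.2 | Does it reach overall malignant neoplasms? |
|---|---|
| Relative risk and 95% CI for each AESI | No. Section 11.6.3 defines malignant neoplasms separately from the AESI list; only thyroid, haematologic and pancreatic cancer are AESIs. |
| Relative risk and 95% CI for each common SAE | No. It works by single Preferred Term at 2% or more, not on a pooled grouping. |
| Model Results Presentation row | No. It covers time-to-event and change-from-baseline endpoints; this is a subject-level incidence comparison. |

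No planned output for the pooled grouping includes an effect estimate or interval.

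**Step 2: the SAP's own design figure.** The only one is 611 MACE events (Section 1): 90% power, margin 1.3, true hazard ratio 1.0, two-sided 0.05.

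Events = 4 × (1.96 + 1.2816)² / (ln 1.3)² = 610.6, rounded up to 611.

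It reproduces. No such figure is given for malignancy.

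**Step 3: what a p-value alone would leave unsaid.**

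Inputs:
- n = 4700 per arm, from about 9400 subjects allocated 1:1 (Section 1). The safety population may be slightly smaller.
- Two-sided 0.05. This is assumed, since no level is stated for the malignancy test.
- Placebo cumulative incidence p0. It is not in the SAP, so it is assumed and ranged from 1% to 5%.
- Observed relative risk 1.20, chosen for illustration, so p1 = 1.2 × p0.

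Formulas (unstratified log-RR Wald approximation):
- SE = √[(1 − p0)/(n·p0) + (1 − p1)/(n·p1)]
- z = ln(1.20)/SE
- Upper limit = 1.20 × exp(1.96 × SE)

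At p0 = 2%: n·p0 = 94 and n·p1 = 112.8. SE = √(0.980/94 + 0.976/112.8) = 0.138. z = 0.1823/0.138 = 1.32, so p = 0.19. Upper limit = 1.20 × exp(0.271) = 1.57.

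| Assumed placebo incidence | SE | p at observed RR 1.20 | Upper 95% limit |
|---|---|---|---|
| 1% | 0.196 | 0.35 | 1.76 |
| 2% | 0.138 | 0.19 | 1.57 |
| 3% | 0.112 | 0.10 | 1.50 |
| 5% | 0.086 | 0.03 | 1.42 |

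**Step 4: the worst result that still misses significance.** With the same n and a pooled two-proportion z-test, the largest non-significant observed relative risk is about 1.43, 1.30, 1.24 and 1.18 at 1%, 2%, 3% and 5%. The corresponding upper 95% limits are 2.07, 1.69, 1.54 and 1.40. Even with an observed relative risk of exactly 1.0, the upper limit would be about 1.50, 1.33, 1.26 and 1.19. What a non-significant result excludes thus depends heavily on the event count, and the test output does not show it.

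**The case against.** The strongest reply has four parts.

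- **Other cancer evidence is planned.** Thyroid, haematologic and pancreatic cancers each get a relative risk with 95% CI in Tables 3.039 and 3.040, and cancer deaths count in the all-cause mortality hazard ratio. A reader might infer that the Mantel-Haenszel p-value is the only comparative evidence on cancer safety. The SAP does not support that. The gap is confined to the pooled grouping.
- **The counts are tabulated.** Tables 3.136 and 3.137 give subjects and events by arm, so a crude relative risk and interval can be worked out by hand. This is true, but it is not the stratum-adjusted estimate that matches the planned test, and its choice would be made after unblinding.
- **Power is not the defect.** A reader might infer that the test will often miss a relevant harm. That needs a malignancy rate and a relevant relative risk, and the SAP gives neither. Under the same assumptions a true relative risk of 1.3 is missed 72%, 51%, 33% and 12% of the time at 1%, 2%, 3% and 5% incidence; a true relative risk of 2.0 is missed at most about 2% of the time. Adding an interval does not change these figures either.
- **Overall malignancy is not a listed endpoint or AESI, and the SAP nowhere treats non-significance as proof of safety.** Both are correct, and they limit the severity. Blank programming notes also prove little alone: Tables 2.24–2.28 are blank too, although Section 8.1.2 commits to hazard ratios and intervals for them. For malignancy, however, the text of 8.2.2 makes no such commitment.

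**Conclusion.** The point holds for the pooled malignant neoplasm grouping and no further. Its planned inferential comparison is a test with no estimate or interval, while AESIs and common SAEs in the same section have both. The consequence is that the planned comparison cannot say how large an excess of overall malignancy is excluded.

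The numerical size is illustrative. The 1.57 limit rests on 4700 per arm, an assumed 2% placebo incidence, an observed relative risk of 1.20 and an unstratified Wald approximation. It moves from 1.76 to 1.42 as the assumed incidence goes from 1% to 5%, and at 5% the same relative risk would be significant. The omission itself depends on none of these assumptions.

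The primary MACE analysis is unaffected.

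**What to change.** In Section 8.2.2, and in Tables 3.139, 3.141, 3.143 and 3.145, add the stratum-adjusted Mantel-Haenszel common relative risk (albiglutide/placebo) with its 95% CI, reported alongside the test p-value. Extend Table 7 note [19] to match. SAS FREQ can give this estimate and its limits in the analysis already planned, with the same data and strata. Name the type of limits, because the exact unconditional interval specified elsewhere in 8.2.2 is described for unstratified relative risks.

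No decision rule on the upper limit is proposed: the SAP has no margin for malignancy, and a rule without one would decide nothing.

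The cost is one sentence and two extra columns in four tables. The one drawback is that an interval may look less reassuring than a p-value alone.
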